1.2 Specific Aims

The primary objectives of this study are as follows:

1. To determine the efficacy of targeted kudzu versus placebo in reducing binge drinking, as determined by number of binge drinking days in timeline follow-back (TLFB), by treatment arm.
2. To determine the efficacy of targeted kudzu versus placebo in reducing recent alcohol consumption, as determined by the proportion of ethyl glucuronide (EtG) positive urines, by treatment arm.
3. To determine the efficacy of targeted kudzu versus placebo in reducing alcohol-associated sexual risk behaviors and incidence of STIs, as determined by audio computer assisted survey instrument (ACASI) data and STI (syphilis, *Neisseria gonorrhoea*, *Chlamydia trachomatis* testing, HIV) testing, by treatment arm.
4. To evaluate the tolerability and acceptability of targeted kudzu versus placebo, as determined by adverse clinical event rates and medication adherence (via data from MEMs cap dispenser monitoring and self-report from SMS texts and TLFB), by treatment arm.

1.3 Facilities and Investigator.

Study activities will take place at the Center on Substance Use and Health (CSUH) of the San Francisco Department of Public Health (SFDPH), a well-established clinical trial site. [name] has a joint appointment as a Senior Research Scientist at SFDPH. He has conducted research at this field site since 2008. The site is centrally located near multiple transit lines with convenient access for residents of multiple neighborhoods with high rates of alcohol use. We have had remarkable success recruiting and retaining alcohol and substance users at this location. Study staff have access to both **SFDPH** and **University of California, San Francisco**. The paired effort of these institutions has proven highly effective in both research and clinical care in San Francisco.

1.3.a. Form 1572

See Appendix B

1.3.b. Sponsor-Investigator

[name], MPH (See Appendix C for CV)

1.3.c. Sub-Investigator

[figure not shown]
[name] (See Appendix D for CV)

1.3.d. Form FDA 3454

See Appendix E

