***Aim 4:** To evaluate the tolerability and acceptability of targeted kudzu versus placebo*, as determined by adverse clinical event rates and medication adherence (via data from MEMs capmonitoring and self-report from EMA and TLFB), by study arm. While laboratory studies have demonstrated the tolerability and acceptability of daily kudzu, we will examine these outcomes in an outpatient setting for targeted (prn) dosing. Adverse clinical events (AEs) and other binary safety outcomes will be presented as percent of participants that experience the safety outcome by treatment arm. Binary adverse effect measures will be analyzed using exact methods, since they are expected to be uncommon. We will measure the acceptability of kudzu among participants by determining medication adherence via MEMs cap opening events, pill count and self-report. Adherence measures of interest will include percent of doses taken during reported drinking days, patterns of adherence and time to stopping medication. We will assess how these measures of adherence track with patterns of alcohol use and binge drinking as reported in TLFB. GEE logistic models will be used to estimate the proportions of kudzu participants taking medication during periods of reported alcohol use and binge drinking. Concordance of adherence measures based on MEMs cap and self-report measures will be examined using weighted Kappa and correlations.

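### Aim 4 promises an adherence comparison of kudzu with placebo, but the only model with adherence as its outcome covers kudzu participants and yields no arm contrast

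*Combined protocol and SAP*

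**What the plan says.** Section 1.2 lists four primary objectives. The fourth is "To evaluate the tolerability and acceptability of targeted kudzu versus placebo, as determined by adverse clinical event rates and medication adherence", with the sources of adherence data named and the comparison made by treatment arm. Section 1.7, Aim 4, restates the objective and ends it the same way: "self-report from EMA and TLFB), by study arm".

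The analysis text in section 1.7, Aim 4, then splits in two:

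- **Tolerability.** Adverse events and other binary safety outcomes are shown as percentages by treatment arm, with exact methods for binary adverse effects.
- **Acceptability.** "We will measure the acceptability of kudzu among participants by determining medication adherence via MEMs cap opening events, pill count and self-report". The measures are listed as follows: "Adherence measures of interest will include percent of doses taken during reported drinking days, patterns of adherence and time to stopping medication". The plan adds: "We will assess how these measures of adherence track with patterns of alcohol use and binge drinking as reported in TLFB". The model is then given: "GEE logistic models will be used to estimate the proportions of kudzu participants taking medication during periods of reported alcohol use and binge drinking". Agreement between dispenser and self-report measures is to be examined by weighted kappa and correlations.

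Section 1.5.e has both kudzu and placebo dispensed in MEMs containers. The section on measures of adherence describes the weekly modified TLFB, daily texts, pill counts and dispenser records for the study as a whole, without restricting them to one arm. The as-treated paragraph of section 1.7 says that the dispenser-opening measure is defined for placebo as well.

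**The concern.** The objective is comparative and the model is not. A kudzu-only proportion describes how often people assigned to kudzu dosed when they drank. It cannot say whether that is more or less often than with placebo.

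The placebo arm is what gives the proportion its meaning. Both arms share the four-capsule dose, the as-needed instruction, the weekly counselling and the daily texts. Without the placebo figure, low adherence in the kudzu arm could reflect the product or the regimen, and the reader cannot tell which. A report that follows section 1.7 to the letter would leave the adherence half of a stated primary objective unanswered, even though the data to answer it are in hand.

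**Working it through.** No stated figure exists to reproduce: section 1.7 gives detectable effects for Aims 1 to 3 and none for Aim 4. The check is therefore mainly textual.

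**Step 1. Does any adherence analysis in section 1.7 give a kudzu-placebo contrast?**

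| Item in section 1.7 | Role of adherence | Arms | Contrast specified? |
|---|---|---|---|
| GEE logistic model, Aim 4 | Outcome | Kudzu only | No |
| Percent of doses on drinking days, patterns, time to stopping | Outcome, listed | Not stated | No method given |
| Tracking with TLFB drinking | Descriptive association | Not stated | No |
| Weighted kappa and correlations | Agreement between measures | Not stated | No |
| As-treated analysis | Time-dependent covariate in an efficacy model | Both | Of the efficacy effect, not of adherence |

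The last row is the only place where placebo adherence data are explicitly used, and adherence is not the outcome there.

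**Step 2. Is the narrowing peculiar to adherence?** Yes. Aim 3 compares STI incidence between the two arms by GEE logistic regression, and the adverse-event text in Aim 4 is by arm. Only the adherence model names one arm.

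**Step 3. What could a contrast show?** This is an illustration, not a figure of the plan.

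- From the documents: 120 participants, 1:1 allocation and 80% retention at 12 weeks, so 120 × 0.80 / 2 = 48 per arm (60 per arm with no loss).
- Borrowed from Aim 1: two-sided 5% level and 80% power.
- Assumed: one binary adherence result per person and reference adherence p₁ of 50-80%.

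The detectable difference d = p₁ − p₂ solves d = 1.96·√(2p̄(1−p̄)/n) + 0.8416·√([p₁(1−p₁) + p₂(1−p₂)]/n), where p̄ is the mean of the two proportions. With p₁ = 0.50, p₂ = 0.228 and n = 48, the right-hand side is 1.96 × 0.0982 + 0.8416 × 0.0942 = 0.272, which matches d.

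The one-arm 95% half-width is 1.96·√(p(1−p)/n). The half-width for a difference between two arms with equal p is √2 times that.

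| Assumed adherence | Detectable difference, 48 per arm | Detectable difference, 60 per arm | Kudzu-only half-width, n = 48 | Difference half-width, 48 per arm |
|---|---|---|---|---|
| 50% | 27.2 points | 24.6 | 14.1 | 20.0 |
| 60% | 28.2 | 25.3 | 13.9 | 19.6 |
| 70% | 28.1 | 25.1 | 13.0 | 18.3 |
| 80% | 26.7 | 23.6 | 11.3 | 16.0 |

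Repeated drinking days per person would change these figures by an amount that depends on a within-person correlation that the documents do not give for adherence.

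**The case against.** The best defence is that a by-arm analysis is plainly intended. The Aim 4 statement says so twice, section 1.7 opens by assigning GEE to treatment effects on repeated outcomes, and Table 3 lists adherence among the outcome variables. On that view the phrase about kudzu participants is loose drafting in a study that section 1.1 calls a pilot. The intent can be granted, and adherence may well be tabulated by arm. But no contrast is written down, and the sentence that specifies the model says the opposite. If both arms were meant, the sentence still needs correcting.

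A second defence is that acceptability belongs to kudzu alone, as the wording "We will measure the acceptability of kudzu among participants by determining medication adherence via MEMs cap opening events, pill count and self-report" suggests. That is a defensible target, but it is not the objective in section 1.2, which reads "To evaluate the tolerability and acceptability of targeted kudzu versus placebo".

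A third is that comparing arms on drinking days conditions on something that kudzu is meant to change. This stands. It limits what the contrast can prove and is carried into the fix. It does not justify leaving the contrast out.

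A reader might also go further and infer that, because doses are tied to expected drinking, time to stopping counts people who merely drink less as having stopped, so that an effective drug looks less acceptable. The documents do not support this. They mention "patterns of adherence and time to stopping medication" once, with no event definition, gap length or censoring rule. Stopping could mean self-reported stopping, the last dispenser opening, or being taken off medication for intolerance, which the protocol's text on minimising side-effect risks allows. Only a rule based on absence of use would have that effect, and the plan adopts none. The first measure listed, percent of doses on reported drinking days, is already conditional on drinking, so drinking less does not by itself lower it.

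**Conclusion.** The point holds for the adherence half of Aim 4. A primary objective is stated as kudzu versus placebo, and its only outcome model, as written, produces no kudzu-placebo contrast. This rests on the text and needs no assumption.

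Its reach is limited. Aims 1 to 3 and the adverse-event half of Aim 4 are untouched, and the placebo data are not missing; what is missing is a specified use of them. On the illustrative assumptions (one binary result per person, 50-80% adherence, 48 retained per arm), only differences of about 27-28 points would have 80% power. The contrast should be read as an estimate with its interval, and a non-significant result should not be taken as evidence of equal acceptability.

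On time to stopping, the most that can be said is that the term is undefined for as-needed dosing. It could misclassify reduced drinking as discontinuation if it were read from absence of dispenser openings. No size can be put on that without a rule that the plan does not contain.

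**What to change.** In section 1.7, Aim 4, replace the kudzu-only sentence with a GEE logistic model fitted in both arms. The outcome is whether a dose was taken on a reported drinking day (yes/no), with a treatment-arm term and robust standard errors. Report each arm's proportion and the arm difference with its 95% CI, obtaining the difference from the model-based proportions because the logistic model itself gives an odds ratio. State which data source defines a dose taken.

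State the limitation with it: drinking days are a post-randomisation outcome, so the two arms may contribute different people and different numbers of days. Report drinking-day counts by arm beside the adherence result and label the contrast descriptive.

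If the team does not want the contrast, the alternative is to restate the adherence part of Aim 4 as descriptive in the kudzu arm, in sections 1.2 and 1.7 alike. If time to stopping is kept, add a line defining the event and the censoring.

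The cost is a few lines of SAP text, to be settled before unblinding. No new data are needed.

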APPENDIX A: Form 1571

APPENDIX B: Form 1572

APPENDIX C: Sponsor-Investigator

Appendix D: Sub-Investigator CV

APPENDIX E: Form 3554

APPENDIX F: Form 3674

APPENDIX G: Manufacture's Letter Of Support

APPENDIX H: COA and BSE/TSE

APPENDIX I: Investigational New Drug Label

CAUTION:

New Drug

Limited by Federal (or United States) law to investigational use only.

Study medication for “A-HACK Study: Addressing Heavy Alcohol use Consumption with Kudzu”

Capsules, 500 mg

May contain: Kudzu 500 mg, or PLACEBO
